### 3. METHODOLOGY:

1. **Type of Study:** Randomized controlled trial.
2. **Study Setting:** NICU of Ain Shams University. Children hospital, Cairo, Egypt.
3. **Study Period:** Two years , from September 2021 till September 2023.
4. **Study Population:** Preterm neonates with RDS requiring noninvasive ventilation, the involved study group will be of matched gestational, postnatal age and sex.
5. **Inclusion Criteria:**
  - Preterm neonates with gestational age  $\leq$  35 weeks with RDS that need noninvasive ventilatory support primarily.
  - 6. Diagnosis of RDS is by clinical presentation, including signs of respiratory distress, ABGs showing hypoxemia and hypercapnia and chest x-ray showing diffuse atelectasis classically described as having a ground-glass appearance . (*Hermansen and Mahajan ,2015*).
  - 7. The need for noninvasive ventilation in the following situations :
    - Preterm with mild to moderate respiratory distress, Silverman score <6 (*Silverman and Anderson,1956*).
    - Mild to moderate hypoxemia (Fio2 less than 50% to maintain SpO2 (90%-94%)
    - Mild to moderate respiratory acidosis (PaCO2<65mmHg with pH>7.20)
    - Apnea (not associated with bradycardia, not needing bag and mask ventilation)
  - 8. **Exclusion Criteria:**
    1. Patients with major upper or lower airway anomalies.
    2. Patients with significant congenital anomalies including cardiac, abdominal or respiratory.
  - 9. **Sample size:** 90 participants
  - 10. **Sample size calculation:**

Sample size was calculated using One-way ANOVA F-test with significance level 0.05. Calculation according results from a previous study (*Abdelhady et al.,2008*) produced a sample size of 30 cases in each group.

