## 2. AIM/ OBJECTIVES

1. Primary aim is to evaluate the efficacy of NHFOV and Hi-VNI Vapotherm in comparison to nasal CPAP as a primary noninvasive respiratory support in preterm neonates through assessment of:
  - The need for invasive mechanical ventilation (IMV) during the first 72 hours after enrollment in one of the groups, days of hospitalization, days on noninvasive respiratory support, days on supplemental oxygen, mortality, severe retinopathy of prematurity(ROP), air leak syndromes, intraventricular hemorrhage(IVH), necrotizing enterocolitis(NEC), nasal trauma and BPD.
2. Secondary aim is to assess haemodynamic changes during periods of non-invasive respiratory support including echocardiographic, cerebral blood flow and mesenteric blood flow changes.

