### 11. Sampling Method:

Preterms will be allocated randomly to one of 3 groups :

- Group A: it will include 30 preterm neonates on NHFOV

- Group B: it will include 30 preterm neonates on Hi-VNI Vapotherm.
- Group C: it will include 30 preterm neonates on nasal CPAP

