## 12. Study Procedures:

1. Detailed antenatal, natal and postnatal history. Gestational age will be estimated using the date of the last menstrual period and confirmed by the new Ballard scoring system (**Ballard et al., 1991**).
2. Full clinical examination including: chest, cardiac, abdominal, neurological examination and anthropometric measurements.
3. Patients' ages, mean arterial blood pressure, urinary output, temperature, capillary refilling time and O2 saturation by pulse oximetry and according, Oxygen Saturation Index (OSI) will be calculated as a noninvasive predictor of respiratory failure (**Muniraman et al., 2019**).
4. Daily inspection of infants' nostrils to evaluate the presence of skin alterations, nasal injury score will be used (**Khan et al., 2017**).
5. Surfactant if given with recording its timing and doses, Curosurf®; Chiesi pharmaceuticals, Parma, Italy. At a dose of 200 mg/kg will be administered via the INSURE method if an infant present with the following:
  - ≤30 weeks GA when FiO2 requirement >0.30 or >30 weeks GA when FiO2 requirement >0.40. In the INSURE technique, surfactant is administered via an endotracheal tube and after a brief period of positive pressure ventilation, patients will be extubated to the assigned mode. (**Zhu et al., 2018**).
6. Caffeine citrate; Chiesi Pharmaceuticals, Parma, Italy. Will be administered when infants present with significant apnea (defined as three or more episodes in 24 hrs or a single episode requiring resuscitation and bag and mask ventilation). The initial loading dose is 20 mg/kg, and the maintenance dose is 5 mg/kg per day (**Zhu et al., 2018**).
7. Assessment of feeding; method (parenteral or enteral) and detecting the type of milk, volume and duration to reach full enteral feeding together with recording presence of any feeding intolerance.
8. Recording of patients' days of hospitalization, days on noninvasive respiratory support, days on supplemental oxygen, initial settings and modifications, inotropic support, sepsis, incidence of ROP, air leak syndromes, IVH, NEC, BPD (**Jobe and Bancalari, 2001**) and mortality.

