### Candidates will be randomized into one of 3 groups :

**A. NHFOV group:** NHFOV will be delivered by; SLE 6000 device, Wipro GE Healthcare Private Limited, Bengaluru, Karnataka. Amplitude range (20:35), frequency range (8-12)HZ, MAP range (6: 10) cmH2O and I:E ratio 1:1 may change to 1:2 in case of air trapping .

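### The plan says the study group will be matched on gestational age, postnatal age and sex, but describes only random allocation and names no covariate; adjusting continuous outcomes for gestational age would gain precision at almost no cost

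*Combined protocol and SAP*

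**What the plan says.** All references are to the combined protocol and SAP.

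- Section 3 (Methodology), item 4, Study Population: "the involved study group will be of matched gestational, postnatal age and sex".
- Item 11, Sampling Method: "Preterms will be allocated randomly to one of 3 groups". Each arm has 30 infants; for group A, "it will include 30 preterm neonates on NHFOV". The later allocation heading repeats "Candidates will be randomized into one of 3 groups". No stratification, minimisation or matched sets are described.
- Item 10, Sample size calculation: "Sample size was calculated using One-way ANOVA F-test with significance level 0.05". No covariate enters it.
- Item 15, Statistical Analysis: summary statistics and a 0.05 threshold. No covariate is named, and no between-arm test either.
- Item 12, Study Procedures: "Gestational age will be estimated using the date of the last menstrual period", confirmed by the Ballard score. Gestational age is thus to be available for every infant. The same item changes the surfactant criterion at 30 weeks.
- Section 2, Aim/Objectives: besides invasive mechanical ventilation (IMV) in the first 72 hours, the primary aim lists "days of hospitalization, days on noninvasive respiratory support, days on supplemental oxygen". The secondary aim is haemodynamic, and its blood-flow measurements are also continuous.

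**The concern.** Taken literally, 'matched' describes a different design, with allocation in matched sets and an analysis that respects them. Taken loosely, as 'comparable', it promises a balance that simple randomisation into arms of 30 makes likely on average but does not ensure. On either reading the plan has no step that acts on these factors.

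Eligibility covers every gestational age up to 35 weeks with no stated lower limit, so infants may differ widely on this variable. If the arms differ in gestational age by chance, no planned analysis separates that gap from a treatment effect. Even without a visible gap, leaving out a prognostic baseline variable that is already collected wastes precision in a small trial.

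**Working it through.** **1. The plan's own figure.** The 30 per group cannot be reproduced, because effect size, standard deviation and power are not stated. Working backwards with the noncentral F distribution (3 groups, N = 90, df 2 and 87, noncentrality 90f²), 30 per group detects f = 0.333 at 80% power, 0.382 at 90% and 0.422 at 95%. The calculation contains no covariate.

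**2. How far randomised arms of 30 can differ by chance.** The standard error of the difference in mean gestational age between two arms is √(2/30) = 0.258 SD. One given pair differs by more than 0.5 SD with probability 5.3%; some pair among the three does so with probability 12.8%. A 0.5 SD gap moves an unadjusted continuous outcome by 0.5r SD, where r is the correlation with gestational age: 0.15, 0.25 or 0.35 SD for assumed r of 0.3, 0.5 or 0.7. The expected gap is zero, and the ordinary standard error already allows for it.

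**3. Gain from adjusting continuous outcomes.** Relative to the unadjusted comparison, the variance is multiplied by (1 − r²)(1 + 1/85). The second term is the average cost of estimating one covariate slope. Effective size per arm is 30 divided by this factor.

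| Assumed r | Variance factor | Effective infants per arm |
|---|---|---|
| 0 | 1.012 | 29.7 |
| 0.2 | 0.971 | 30.9 |
| 0.3 | 0.921 | 32.6 |
| 0.5 | 0.759 | 39.5 |
| 0.7 | 0.516 | 58.1 |

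The same gain expressed as power: start from f = 0.333 (80% unadjusted), use f/√(1 − r²) and df 2 and 86. ANCOVA power is 80.0% at r = 0, 83.8% at 0.3, 90.4% at 0.5 and 98.0% at 0.7.

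**4. IMV within 72 hours.** The documents give neither the gestational-age mix nor failure rates by gestational age, so both are assumed. Take failure on CPAP at ≤30 vs >30 weeks as 30% vs 15%, 40% vs 10% or 60% vs 10%, and a 65% relative reduction in the active arm. Simulated power for one active arm against CPAP under simple allocation, unadjusted chi-square to Cochran-Mantel-Haenszel (CMH) over the two strata:

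| Share ≤30 weeks | 30% vs 15% | 40% vs 10% | 60% vs 10% |
|---|---|---|---|
| 20% | 29.9% to 27.5% | 26.8% to 25.2% | 33.0% to 34.9% |
| 40% | 34.3% to 33.0% | 35.7% to 36.3% | 47.4% to 54.7% |
| 50% | 36.4% to 35.5% | 39.8% to 41.3% | 55.8% to 63.0% |

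The change runs from a loss of about 2 points to a gain of about 7. With no true effect and a 40% share, type I error over all trials is about 5% for both tests.

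**5. What a gap does to IMV.** At a 40% share, one given pair differs by at least 20 points in the proportion ≤30 weeks in 15% of trials. A gap of exactly 20 points shifts the risk difference by 0.20 × 0.15 = 0.03, 0.20 × 0.30 = 0.06 or 0.20 × 0.50 = 0.10. The standard error is √(2m(1 − m)/30). With overall risk m = 0.21, 0.22 or 0.30 it is 0.105, 0.107 or 0.118, so the shift is about 0.3, 0.6 or 0.8 of a standard error.

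The two-stratum cut does not remove this completely. With gestational age assumed uniform over 27 to 35 weeks and risk changing smoothly, in trials with a mean gap above 0.5 SD, unadjusted shifts of 0.039, 0.077 and 0.117 fall to 0.010, 0.020 and 0.026. About a fifth to a quarter remains.

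**6. Multiplicity.** Two CMH tests against the shared CPAP arm, each at 0.05, give a familywise error of about 9%.

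**The case against.** The strongest reply is that the defect is one loose word. 'Matched' stands under Study Population in a document that calls itself a randomised controlled trial, and nothing else depends on it. Read as 'comparable at baseline', it is harmless. The missing covariate is also partly a by-product of a larger gap, since item 15 names no between-arm test at all. Much of this stands: correcting the word alone would be clerical. What survives is that a baseline variable the plan itself singles out, and already records, is left unused for continuous outcomes.

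Three stronger readings are tempting, and the documents do not support them.

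- *A reader might infer that the comparison is biased or invalid because the promised matching is absent.* It is not. Allocation is random, so imbalance arises by chance with expected value zero.
- *A reader might infer that false positives are inflated.* Among trials with a gap of at least 20 points (40% share), the unadjusted chi-square test is falsely significant in 5.8%, 8.7% or 13.5% across the three scenarios. In the remaining trials it is conservative: 4.7%, 4.2% and 3.3%. Weighting by 15% and 85% gives about 4.9%, 4.9% and 4.8%. The conditional rates are not the trial's error rate.
- *A reader might infer that IMV must be adjusted for gestational age.* The change in surfactant criterion at 30 weeks shows that gestational age affects care, not how strongly it predicts IMV. Under weak prognosis or a small ≤30-week share, CMH loses power.

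**Conclusion.** The point holds as a minor improvement. The plan states a matching that it has no means to deliver, and it omits gestational age from the analysis although the variable is already collected. The consequence is lost precision and less protection against a chance imbalance.

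The firm part concerns continuous outcomes. Across assumed correlations of 0.2 to 0.7, adjustment is worth between about 1 and 28 extra infants per arm (30.9 to 58.1 against 30); if gestational age is unrelated to the outcome, the loss is about 0.3 of an infant per arm. The size depends wholly on the correlation, which will differ by outcome and is not in the documents.

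For IMV the evidence supports only an optional supporting analysis. Stratifying the randomisation is not part of this point: the stated study period ended in September 2023, so it may no longer be possible.

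**What to change.** 1. In Study Population, replace 'matched' with 'randomised'.
2. In Statistical Analysis, prespecify gestational age in weeks as a covariate for between-arm comparisons of continuous outcomes, that is, ANCOVA in place of one-way ANOVA. Analyse skewed day counts on a log scale, with a stated rule for zeros.
3. Optionally, for IMV within 72 hours, add a CMH comparison of each active arm with CPAP over ≤30 vs >30 weeks (the cut the surfactant criterion already uses), reported as supporting. State a multiplicity rule for the two comparisons, for example Holm.
4. If the data have already been seen and the adjustment was not fixed beforehand, label the adjusted analysis post hoc.

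Cost: one changed word, one or two sentences and one residual degree of freedom (87 to 86), with no new data or patients. If item 3 is adopted, the stratified IMV test may lose about 2 points of power when gestational age is weakly prognostic or few infants are ≤30 weeks.

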### **C. Standard noninvasive mechanical ventilation group (CPAP):**

CPAP will be delivered by; MEDIN CNO device, medin Medical Innovations GmbH, Olching, Germany . Pressure ranging from 5 to 8 cm H2O,to maintain target oxygen saturation (SpO2) from 90% to 94%.

**We will define failure of non-invasive mode and need for invasive mechanical ventilation according to the following while on the maximum noninvasive settings :**

- Severe respiratory acidosis (PaCO2 ≥ 65 mmHg with pH ≤ 7.20),
- Severe apnea and bradycardia (defined as recurrent apnea with >3 episodes per hour associated with heart rate <100/min or a single episode of apnea that requires bag and mask ventilation)
- Hypoxemia (FiO2 >0.5 to maintain SpO2 90% to 94%)
- Severe respiratory distress characterised by retractions, moaning sounds or nasal flaring (defined as Silverman score >6) (*Silverman and Anderson, 1956*).
- Pulmonary haemorrhage and Cardiopulmonary arrest needing chest compressions (*Shi and De Luca, 2019*).

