### **14. Radiological investigation**

- A. Chest X-ray with radiological assessment of grades of RDS.
- B. Echocardiography : Two dimensional Echocardiography will be done using Vivid 9,GE Ultrasonography machine (Norway) with 6 MHz transducer frequency.To assess any structural cardiac anomalies, the patency of ductus arteriosus, right ventricular output (RVO), left ventricular output (LVO), and superior vena cava (SVC) flow.
- C. Transcranial ultrasonography by; Samsong Medison Co ,Korea. Doppler applied to the major cerebral arteries to provide an estimate of cerebral blood flow .
- D. Assessment of pre-prandial superior mesenteric artery (SMA) velocity and volume of blood flow with Doppler sonography by; Samsong Medison Co ,Korea.

**15. Statistical Analysis:** Numerical data will be summarized using mean and standard deviations or medians and inter quartile ranges. Qualitative data will be presented as count and percentage, p-value <0.05 will be considered significant.

**16. Statistical Package:** Statistical analysis will be performed with statistical package for social science (SPSS)

**17. Ethical Considerations:** A written informed consent will be taken from the parents or legal guardians before enrolment, after fully explaining to them the nature of the study. The approval of the Research Ethics Committee at Ain Shams University will also be obtained.

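### Eleven unranked outcomes share the primary aim with p<0.05 as the only decision rule, and 30 per group is not tied to any of them, including invasive ventilation within 72 hours

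*Combined protocol and SAP*

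**What the plan says.** Section 2 (Aim/Objectives), item 1, sets out the primary aim as one list of eleven outcomes. It opens with "The need for invasive mechanical ventilation (IMV) during the first 72 hours after enrollment in one of the groups", continues with "days of hospitalization, days on noninvasive respiratory support, days on supplemental oxygen", and goes on to mortality, severe ROP, air leak, IVH, NEC, nasal trauma and BPD. No priority is given. The secondary aim is haemodynamic change.

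Section 3, item 10, gives a method, "Sample size was calculated using One-way ANOVA F-test with significance level 0.05", refers to one previous study, and says that the calculation "produced a sample size of 30 cases in each group". It states no variable, effect, SD or power. In the reference list (section 4), the title of that study concerns haemodynamic changes during weaning from nasal CPAP.

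Section 3, item 15, is the whole analysis plan. Numerical data get means or medians with their spread. For the rest, "Qualitative data will be presented as count and percentage, p-value <0.05 will be considered significant". No between-group test, interval estimate, order of testing or multiplicity rule appears.

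Two other places bear on the outcomes. Under item 12, after the CPAP group, the plan lists criteria: "We will define failure of non-invasive mode and need for invasive mechanical ventilation according to the following". In item 12, procedure 4, the nostrils are inspected daily and a "nasal injury score will be used".

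**The concern.** An efficacy claim needs one pre-stated result that decides it. Here there are eleven candidates and two comparisons with CPAP, each judged at 0.05. A trial in which neither new mode does anything has a sizeable chance of a significant result somewhere, and the plan does not say that such a result falls short of efficacy.

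The sample size does not settle which outcome was meant. An ANOVA F-test compares means. By itself it says nothing about adequacy for a yes/no outcome such as IMV. If IMV is what clinicians will look at first, a null result in 30 per arm could be read as equal efficacy when the trial could not tell a large benefit from none.

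**Working it through.** **1. The plan's own figure.** Inputs from items 10 and 11: three groups, 30 each, alpha 0.05. Effect, SD and power are not given, so 30 cannot be reproduced forwards. Solving backwards with the noncentral F (noncentrality 90 f²), 30 per group results from f = 0.333 at 80% power or f = 0.382 at 90%. If one arm differs from two equal arms, the shift is 3f/√2, that is 0.71 SD or 0.81 SD. Many sets of inputs give 30, so the figure can be neither confirmed nor refuted.

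**2. False positives.** Eleven outcomes (section 2), threshold 0.05 (item 15). Assumptions: no true effects, approximately normal test statistics, two-sided pairwise tests against CPAP with no omnibus gate. Two comparisons sharing an equal-sized CPAP arm have correlation 0.5. The chance that at least one of the two is significant is then 9.07% per outcome in either direction, and 4.54% in favour of a new mode.

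For independent outcomes:

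- Either direction, one comparison: 1 − 0.95^11 = 43%
- Either direction, both: 1 − (1 − 0.0907)^11 = 65%
- Favouring a new mode, one comparison: 1 − 0.975^11 = 24%
- Favouring a new mode, both: 1 − (1 − 0.0454)^11 = 40%

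With correlation 0.5 between outcomes (quadrature or simulation):

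| | One comparison | Both |
|---|---|---|
| Either direction | 30% | 49% |
| Favouring a new mode | 15% | 25% |

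A low case: three durations tested at 5%, and eight yes/no outcomes at an assumed 5% event rate tested by Fisher, whose actual error is then 0.15% each. For one comparison, 1 − 0.95³ × (1 − 0.0015)^8 = 15% in either direction. Favouring the new mode, it is 1 − 0.975³ × (1 − 0.00075)^8 = 8%. This case treats nasal trauma as yes/no, which the plan does not establish.

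**3. What 30 per arm can detect for IMV.** The documents give no event rates, so the CPAP rates are assumed. Exact binomial enumeration, Pearson chi-square without correction, two-sided 0.05, 30 vs 30:

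| Assumed CPAP rate | 20% | 30% | 40% | 50% |
|---|---|---|---|---|
| Power if the rate is halved | 19% | 28% | 39% | 52% |
| Rate needed for 80% power | about 1% | about 5% | about 10% | about 17% |

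Fisher's test, or alpha split over two comparisons, gives less. For 30% vs 15%, power is 19% by Fisher at 0.05, 20% by chi-square at 0.025 and 12% by Fisher at 0.025.

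**4. Reading a null result.** As an illustration, 9/30 on CPAP against 4/30 on a new mode is a difference of 16.7 points, with a 95% Newcombe interval of −4 to +36. The chi-square p is 0.12 and the Fisher p 0.21. Such a result is compatible with a large benefit, and item 15 does not say how it would be read.

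**The case against.** The strongest objection is to the size of the harm. The figures of 43% and 65% count differences in either direction, and half of single false positives favour CPAP. A reader might take them as the chance of a false efficacy claim. They are not: the matching figures are 24% and 40%, or 15% and 25% at correlation 0.5. Because no test is named, an omnibus test gating the pairwise ones is also consistent with the plan and would lower the two-comparison figures. With Fisher tests of rare events, one comparison falls to about 8%. All of this stands. It reduces the figures but does not supply a rule for which outcome decides.

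A second objection is that IMV comes first and so is the primary endpoint in all but name. Being listed first is not a designation, and nothing in section 2 or item 15 treats it as one.

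A third is that choosing IMV is a reviewer's preference, for an outcome on which power is poor. That is partly fair. The choice is the sponsor's, and the text supports IMV without compelling it.

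A stronger reading is also tempting: that the trial was sized on a haemodynamic variable and is therefore mismatched to its primary aim. The cited title points that way, since haemodynamics is the subject of the secondary aim. A title does not show which variable was taken from the study, however, and the three durations in the primary aim could also be analysed by ANOVA. A mismatch is not proven.

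**Conclusion.** The point holds and should be fixed. As written, any of eleven outcomes in either comparison can carry the efficacy claim. The chance of a false claim for a new mode is 24% for one comparison and 40% for both under independence, and 15% and 25% at correlation 0.5. These values rest on ungated pairwise tests at two-sided 0.05, and the low case above gives about 8% for one comparison.

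Adequacy of 30 per group for IMV within 72 hours is not shown. A reader might infer that 30 is the wrong number. The documents do not support that, because without the variable, effect, SD and power the figure cannot be checked. What can be said is conditional: at assumed CPAP rates of 20 to 40%, a true halving would be missed in most such trials by chi-square at 0.05, and at 50% in about half.

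**What to change.** Keep 90 infants and change three places.

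1. **Section 2.** By dated amendment, designate one primary endpoint and make the other ten outcomes supportive. IMV within 72 hours is the natural choice: it is listed first, is the only outcome in that list with a time window, and has criteria under item 12. Those criteria do not repeat the 72 hours, so cross-refer. State whether intubation for INSURE (item 12, procedure 5) and death before IMV count as events. The study period runs "from September 2021 till September 2023" and the documents do not show whether data have been seen. The amendment must say so, and must label the choice post hoc if comparisons have already been made.
2. **Item 15.** Report NHFOV vs CPAP and Hi-VNI vs CPAP each as a risk difference with 95% CI. Name the test, state the alpha for each of the two comparisons, and state that p≥0.05 will not be read as equal efficacy.
3. **Item 10.** Name the variable actually used, limit the sizing claim to it, and state what 30 per arm can detect for IMV under the test and alpha chosen in item 15. If that is chi-square at 0.05, the table in step 3 can be used; otherwise recompute it.

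The cost is no extra infants and no new measurements, but it is more than rewording. Ten outcomes can no longer carry the efficacy claim, the stated capability for IMV is unfavourable, and a post hoc designation would carry less weight.
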